- 1. The trial will be stopped if neither active treatment appears to be effective (both active treatment effect sizes are smaller than a minimum clinically important difference, defined as an effect size of 0.25).
- 2. The trial will continue to Stage 2, if there is evidence (based on precision analysis i.e., a smaller interval width) that at least one treatment from the interim analysis at end of Stage 1 is more effective than placebo. If both treatments appear to be effective in Stage 1 then the trial will continue with three-arms. Findings from the interim analysis may result in change in sample size required for achieving statistical

significance at a desired power. At the end of Stage 2, data collected from both stages will be combined for a final analysis. Depending on the results of the interim analysis, blinded sample size re-estimation may be performed per recommendation from the DSMB.

Stage 2 will be a two-arm (assuming that only one promising treatment is retained) randomized study comparing the selected treatments from Stage 1 versus the placebo. At the end of the Stage 2, the selected treatment will be compared with placebo using the number of drinks per drinking day as the primary outcome measure. At each stage, the primary efficacy analysis will be performed based on the intention-to-treat (ITT) population, defined as all randomized participants who have at least one follow-up evaluation regardless of their compliance with the protocol. In case of substantial numbers of protocol violations, a per-protocol analysis may be done to determine whether they influence the conclusions. At end of Stage 2 (or end of trial), a clinical superiority test may be performed after non-inferiority has been established, without paying any statistical penalty.

Sample size re-estimation: Sample size re-estimation will be performed based on the number of drinks per drinking day as the primary outcome measure. Sample size calculations will be performed as follows:¹³²

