At Stage 1, we will recruit 99 subjects (i.e., 33 subjects per arm) with 1:1:1 treatment allocation ratio, which provides clinically meaningful minimum *effect size of 0.25 between each treatment arm and placebo with* a two-sided test at the 5% level of significance. After review of interim data, an additional 100 subjects at 1:1 ratio will be recruited at Stage 2. If the effect size for *both* medications is at least 0.50 at interim analysis then we will have 81.4% power with 66 participants per arm and the study will continue with three treatment arms. To summarize: 1) If neither treatment has an effect size of at least 0.25 at interim analysis then the trial is discontinued. *This effect size was selected because it is a clinically meaningful value. Naltrexone has an average effect size of approximately 0.15-0.20 in clinical trials for alcohol dependence.*¹³³ *Thus, a useful new treatment for alcohol dependence should at least have a larger effect size than the standard treatment. This effect size of 0.25 is also an effect size at interim analysis that provides a reasonable likelihood of a significant difference from placebo at study completion assuming some increase in effect size as more participants are*

enrolled and the variance of the data decreases. 2) If one treatment has an effect size of at least 0.25 then the trial continues dropping the less effective treatment (two-arm study of one medication vs. placebo). 3) If both treatments have an effect size of at least 0.50 then neither treatment is dropped and the trial continues as a three-arm trial (both medications vs. placebo). This assumes that the DSMB assessment determines that the selected treatment(s) has an adequate safety and tolerability profile to continue the trial. We anticipate that the interim analysis will take place at approximately month 26 of the study. As an incentive to enroll quickly and avoid prolonging the study, we will mandate that an interim analysis take place by month 34 even if fewer than 99 participants have been enrolled. All interim analysis decisions will be made in consultation with the NIAAA program official and DSMB.

Statistical Methods:

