The primary analysis is to assess between-group differences in alcohol use measures including drinks per drinking day (primary outcome measure), heavy drinking days, and drinking days using Generalized Estimation Equations (GEEs) analysis with a site effect as a cluster. GEE model has been used in a prescription drug abuse treatment study with multiple site adaptive design (Weiss et al., 2010).¹⁰⁶ Point estimates of the difference in the average of the number of drinks per drinking day between treatment groups and their corresponding 95% confidence intervals will be obtained. A similar analysis will be used to assess exploratory aims 1 (mood), 2 (side effects), and 3 (craving). Length of time in the study in weeks will be compared between groups using Cox proportional hazards regression (SAS Proc PHREG). Assessments only obtained at baseline and weeks 6 and 12 (e.g. GGT, AST, ALT and CDT levels) or baseline and week12 (e.g. cognitive assessments, neurosteroid and choline levels) will be analyzed using analysis of variance (ANOVA). The correlation between the reduction in alcohol use/alcohol craving and reduction in manic and depressive symptoms, and also improvement in cognitive outcomes, will be assessed using Pearson's or Spearman's correlation coefficient. To address exploratory aim 6) "Determine whether changes in alcohol craving, mood or cognition occur before or after changes in alcohol use." a panel model with lagged effects¹³⁴ will be used to analyze 12-week longitudinal data (SAS Proc Panel) in order to explore serial correlations between changes in alcohol use and depressive symptoms or cognitive outcomes with lagged effect (e.g. one week, two week). The panel model will be constructed for each alcohol use, alcohol craving, depressive and manic symptom, and cognitive outcome and test if change in alcohol use follows changes in craving, mood or cognition at subsequent visits and vice versa.

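### The final estimate for a retained drug reuses the Stage 1 data that selected it, so it is biased upward, and no corrected estimate is planned beside it

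*Combined protocol and SAP*

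**What the plan says.** All the relevant text is in section 3.3.c of the combined protocol and SAP.

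- **Stage sizes** (sample size re-estimation): "At Stage 1, we will recruit 99 subjects (i.e., 33 subjects per arm) with 1:1:1 treatment allocation ratio"; afterwards "an additional 100 subjects at 1:1 ratio will be recruited at Stage 2".
- **Selection** (same part): "If neither treatment has an effect size of at least 0.25 at interim analysis then the trial is discontinued"; "If one treatment has an effect size of at least 0.25 then the trial continues dropping the less effective treatment"; "If both treatments have an effect size of at least 0.50 then neither treatment is dropped".
- **Pooling** (General Analytic Plan): "data collected from both stages will be combined for a final analysis".
- **Reporting** (Statistical Methods): GEE analysis giving "Point estimates of the difference in the average of the number of drinks per drinking day between treatment groups", with the matching 95% intervals.
- **Reference value** (sample size re-estimation): naltrexone's average effect size is put at roughly 0.15-0.20, and the 0.25 threshold is justified on the ground that "a useful new treatment for alcohol dependence should at least have a larger effect size than the standard treatment".

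No section gives a Stage 2-only, conditional or bias-adjusted estimate. The predictive confidence interval in the General Analytic Plan serves the Stage 1 selection decision. The sensitivity analyses in section 3.3.d concern missing data.

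**The concern.** A drug reaches the final analysis only after a good Stage 1 result. Averaged over the trials in which it is kept, its Stage 1 estimate exceeds the truth, and pooling carries part of that excess into the final figure. This is a problem of estimation, separate from the type I error of the test: a stricter critical value would leave the point estimate unchanged.

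The plan also expects the effect size to rise somewhat after the interim as more participants are enrolled. For a drug kept because it passed a threshold, the expected movement is downward. Nothing in the plan suggests that this was considered.

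At stake are the reported size of effect for the retained drug, any reading of it against 0.25 or the naltrexone range, and its use as a planning value for later trials. The bias is largest where the true effect is small.

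**Working it through.** **Inputs.** From section 3.3.c: 33 per arm in Stage 1; 50 per arm in Stage 2 if two arms remain (83 combined); 66 per arm in total if three arms continue; the 0.25 and 0.50 rules; two-sided 5%. Assumed, because the documents give no SD for drinks per drinking day: a normal outcome, unit SD and one mean per patient. The true effects are scenarios.

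**The plan's own figure.** Power at effect size 0.50 with 66 per arm: 0.50 × √(66/2) = 2.872, and Φ(2.872 − 1.96) = 81.9%. The noncentral t gives 81.35%, against the stated 81.4%. The unit-SD framework therefore matches the plan's.

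**Analytic check at true effect 0.20, threshold only.**

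1. Stage 1 standard error: √(2/33) = 0.246.
2. Standardised threshold: (0.25 − 0.20)/0.246 = 0.203.
3. Chance of passing: 1 − Φ(0.203) = 0.420.
4. Mean Stage 1 estimate given passing: 0.20 + 0.246 × φ(0.203)/0.420 = 0.429.
5. Pooled mean: (33/83) × 0.429 + (50/83) × 0.20 = 0.291, a bias of +0.09.

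**Simulation of the full rules.** Shared placebo arm, 2,000,000 trials per scenario, both drugs with the same true effect. Two-arm continuations:

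| True effect | Mean bias, pooled | 95% CI coverage | RMSE, pooled | RMSE, Stage 2-only |
|---|---|---|---|---|
| 0 | +0.15 | 88% | 0.199 | 0.200 |
| 0.20 | +0.09 | about 94% | 0.160 | 0.200 |
| 0.25 | +0.08 | 95% | 0.153 | 0.200 |
| 0.50 | +0.01 | 97% | 0.137 | 0.200 |

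**How often each path occurs.** With both effects at 0 the trial stops at the interim in 75% of cases. With both at 0.20 it stops in about 42%, continues with two arms in about 54% and with three in about 4%.

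**Detail at 0.20.** The pooled point estimate exceeds 0.20 in about 76% of two-arm continuations, against 50% for Stage 2 data alone. The lower confidence limit lies above 0.20 in about 5.5%, and the upper limit lies below it in about 0.1%.

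**Three-arm path.** The bias is about +0.20 with both drugs at 0.25 (6% of trials) and +0.11 with both at 0.50 (33% of trials).

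**Sensitivity of the 0.29 mean at true 0.20, two-arm path.**

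- Other drug's true effect 0 instead of 0.20: 0.291.
- About 70% of patients contributing (23 then 35 per arm): 0.305.
- A smaller Stage 1 (assumed 25 then 62 per arm): 0.273.
- General Analytic Plan read as keeping three arms whenever both drugs reach 0.25: 0.275 with two arms, 0.328 with three.

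**Precision.** Pooled SE: √(2/83) = 0.155. Stage 2-only SE: √(2/50) = 0.200. Ratio: 1.29.

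**The case against.** The arithmetic is not in dispute, but four objections limit what follows from it.

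**The benchmark.** A reader might infer that the trial would declare a drug with true effect 0.20 better than naltrexone. The documents do not support that. The naltrexone range is there to justify the interim threshold; no section schedules a final comparison with it or with 0.25, and the planned estimate is in drinks per drinking day, not SD units. The interval is reported beside the estimate, and a typical result of 0.29 ± 1.96 × 0.155, about −0.01 to 0.59, includes both 0.20 and zero. Only the point estimate would appear to beat the range. This objection stands.

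**Coverage.** A reader might also infer that the 95% intervals fail generally. Coverage is clearly low only near zero effect. At 0.20 the interval is shifted upward and misses almost always on the favourable side, but total coverage is close to nominal. This stands too.

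**Accuracy.** Stage 2 data alone remove the bias, but the RMSE is equal to or higher than that of the pooled estimate in every scenario above. This argues against replacing the pooled estimate. It does not argue against showing a second one.

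**Feasibility.** Conditionally unbiased two-stage estimators such as the UMVCUE need a fixed selection rule and known stage sizes. The plan allows sample size re-estimation, other adaptations on DSMB advice, a safety judgement, and an interim by month 34 with fewer than 99 enrolled. It also describes the three-arm condition in two ways. This stands, and it narrows the remedy. What remains is that the plan, followed as written, reports a biased estimate without a caution or a companion.

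**Conclusion.** The concern holds as a fault in estimation and reporting. Given a two-arm Stage 2, the pooled estimate is too high by about 0.15 SD when neither drug works, 0.09 at a true effect of 0.20 and 0.08 at 0.25; the bias nearly vanishes at 0.50. It is larger in the less common three-arm path.

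The 0.29 at true 0.20 is an average over retained cases. It should not be read as what any drug with that effect would be reported at, since the trial often stops instead.

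The figures assume normality, unit SD, one mean per patient and the stated rules applied as written. Other readings of the rules move the 0.20 result within about 0.27 to 0.33 and leave its direction unchanged. The primary test and analysis need not change, and the correction should be settled before unblinded results are seen.

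**What to change.** 1. Keep the pooled GEE analysis as primary.
2. Pre-specify beside it the Stage 2-only difference and 95% interval, defining Stage 2 as participants whose outcomes did not enter the interim analysis. This estimate is free of the selection bias whatever rule the DSMB actually applies at the interim.
3. Add a conditionally bias-adjusted two-stage estimate only if the selection rule and stage sizes are followed as fixed.
4. State in the SAP that the pooled estimate for a retained drug is subject to selection bias. State also that any interpretation of effect size against 0.25 or the naltrexone range, or any use in planning later trials, will show the Stage 2-only or adjusted estimate alongside it.

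Items 1, 2 and 4 need SAP wording and little programming, with no extra participants or data. The downside is precision: the Stage 2-only interval is about 29% wider (SE 0.200 against 0.155), and at true 0.20 its RMSE is 0.200 against 0.160. That is why it is a companion and not a replacement.

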Among participants with alcohol use disorder (in addition to cocaine), and active alcohol use at baseline (n=14), potentially meaningful changes in alcohol use and craving were observed. Citicoline-treated patients had a significant decrease in alcohol craving based on a 0-100 mm visual analogue scale (-28.7±31.3, p=0.05) while the placebo-treated group showed a much smaller decrease in alcohol craving (-1.9±66.4, p=ns). Despite modest baseline values, alcohol use decreased by 0.9 ± 1.4 days/week in the citicoline group as compared to only 0.4 ± 0.9 days/week with placebo. Heavy drinking days decreased by 0.9 ± 2.1 (p=0.04) days with citicoline as compared to 0.0 ± 0.6 with placebo. Drinks per drinking day decreased by 2.4 ± 11.3 with citicoline and 0.8 ± 2.6 with placebo. In the alcohol use group, RAVLT delayed recall performance increased by 12.4 ± 12.9 points with citicoline (p=0.04), but decreased by 1.8 ± 3.5 points with placebo (Cohen's d = 1.5, large effect size). Significance: Findings suggest reductions in both cocaine and alcohol use with citicoline. Memory improved with citicoline, particularly in those with alcohol use. Citicoline was safe and well tolerated, and was associated with better study retention than placebo.

Pilot Study 2: A 12-week, double-blind, placebo-controlled trial of citicoline add-on therapy in patients with BPD I disorder and cocaine abuse/dependence

Methods: 130 outpatients with BPD (depressed), cocaine dependence and a cocaine-positive urine at baseline were given citicoline or placebo add-on therapy to stable doses of mood stabilizers. Both groups received cognitive behavioral therapy and a contingency management plan of escalating payments for each urine sample provided. These payments were not related to whether the urine drug screen (UDS) was positive. **Results:** Among those with at least one post-baseline visit (n=60 citicoline, n=61 placebo) a group (f=4.5, df=1,1057, p=.0351) and group by time interaction (f=11.2, df=1,1057, p=.0009) was observed. Similar results were observed when imputing missing data as cocaine-positive [treatment group effect (p=.0222), treatment group by time effect (p=.0151)]. Completion rates non-significantly favored citicoline (71% vs. 57%).

In those with alcohol dependence, citicoline (n=33) showed a trend toward a greater decrease in days per week of alcohol use than placebo (n=37) (-3.67±4.11 days vs. -1.86±4.44 days, p=.084).

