At each stage, a table will show the adverse events (categorized by seriousness, severity, and possible association with study drug) ordered by decreasing frequency for all patients. If appropriate, the incidence rate of adverse events will be compared by Fisher's Exact Test. Special attention will be given to those participants who have discontinued due to adverse events or experienced a serious adverse event. Exploratory analyses such as determining if baseline blood neurosteroid or choline levels predict response and whether changes in these levels are associated with clinical response will be conducted using a mixed model (SAS Proc GLIMMIX) with baseline blood neurosteroid and choline levels as fixed effects. In addition, subgroup analyses with respect to patient demographics and characteristics may be performed as deemed appropriate by the PI and/or biostatistician. Unless otherwise noted, tests of hypotheses are 2-sided and the nominal level of significance will be 0.05.

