3.3.d. Dropouts: Retention is challenging in studies involving BPD/schizoaffective disorder and substance dependence. We have greatly improved our retention over the years by implementing 1) more frequent visits, 2) more frequent contact to remind participants of appointments, and 3) the use of a psychosocial platform. To minimize attrition, we will obtain multiple contact numbers, pay participants small sums at each visit, and to the extent possible have the same research coordinator and psychiatrist assess participants at each visit. In addition, data will be analyzed using an analysis that uses all of the available data and allows for missing data. We will also use a contingency management strategy in which participants are given small vouchers that increase in value with consecutive appointments attended and reset following a missed appointment. We included a similar strategy in a recently completed study in BPD and cocaine dependence (Dallas site) and observed substantial improvement in retention. We anticipate that, using the above approach and considering completion rates in both PI's studies, the proposed study will have a completion rate > 70%. Although we will make every effort to minimize missing visits and dropouts, dropouts and missing visits are common in longitudinal studies. Therefore, we will do comprehensive sensitivity analyses to investigate the consequences of incomplete observations in the analysis of repeated measurement data using local influence, pattern mixture models and multiple imputations.¹³⁵⁻¹³⁷

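### ANOVA is named for the biomarkers, blood levels and cognition with no baseline covariate, scale or outcome form; a baseline-adjusted model would be better at no data cost

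*Combined protocol and SAP*

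**What the plan says.** Section 3.3.c (Statistical Methods) assigns GEE to the drinking measures and a similar analysis to mood, side effects and craving. The measures taken less often get a different method. The text groups "Assessments only obtained at baseline and weeks 6 and 12 (e.g. GGT, AST, ALT and CDT levels) or baseline and week12", giving cognitive tests and neurosteroid and choline levels as examples of the second kind, and states that they "will be analyzed using analysis of variance (ANOVA"). Nothing more is said about that model. The reader is not told whether the outcome is the week-12 value, the change from baseline or all visits together. Baseline adjustment, transformation and the handling of missing samples are also left open.

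Three other places bear on this:

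- Section 3.3.d (Dropouts) says "data will be analyzed using an analysis that uses all of the available data and allows for missing data". It adds sensitivity analyses by "local influence, pattern mixture models and multiple imputations" for repeated measurements, and does not limit either to the primary outcome.
- The same section expects that "the proposed study will have a completion rate > 70"%.
- Section 3.3.b.8 repeats the laboratory tests at week 6 and at exit, so some early leavers may give a final sample.

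**The concern.** The plan collects a baseline value for every one of these measures but does not commit to using it as a covariate. If ANOVA is run on week-12 values, baseline is ignored. If it is run on change scores, baseline is used inefficiently unless the correlation between visits is high. If it is run as a classical repeated-measures table, a participant with baseline and week-6 GGT but no week-12 value drops out of the analysis.

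The last case raises validity as well as precision, because the investigators expect citicoline to help keep people in treatment. Section 3.3.a says of Pilot Study 2: "Completion rates non-significantly favored citicoline (71% vs. 57"%). Pilot Study 1 reports completion more than twice as high on citicoline. If a drug changes who reaches week 12, a comparison of completers is no longer fully protected by randomization.

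The laboratory markers are the objective measures of drinking that accompany a self-reported primary outcome, so a needlessly weak analysis of them wastes useful supporting evidence. Leaving outcome form, scale and adjustment open also allows them to be chosen after the results are seen.

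**Working it through.** **Inputs from the documents (section 3.3.c unless stated)**

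- Stage 1 has 33 per arm. Stage 2 adds 100 at 1:1, so a retained arm has 33 + 50 = 83 on the two-arm path. The three-arm path has 66 per arm.
- The effect size behind the stated power is 0.50 ("medications is at least 0.50 at interim analysis"). It belongs to the primary outcome and is borrowed here for illustration.
- On error rate, "tests of hypotheses are 2-sided and the nominal level of significance will be 0.05".
- Completion is taken as 70% (section 3.3.d), which gives 0.70 × 83 ≈ 58 or 0.70 × 66 ≈ 46 per arm with week-12 data.

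**Assumptions, not in the documents:** baseline-to-week-12 correlation ρ of 0.3 to 0.8; log-scale SD of 0.25 to 1.2.

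**Step 1. The plan's own figure.** A two-sample t test with d = 0.50, n = 66 per arm and noncentrality 0.5 × √(66/2) = 2.87 gives 81.35% power. The plan states 81.4%, so its figure reproduces. The plan states no power for the ANOVA endpoints.

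**Step 2. Baseline adjustment.** Let the week-12 value have variance 1. The variance that counts is then 1 for ANOVA on the week-12 value, 2(1 − ρ) for ANOVA on change, and 1 − ρ² for ANCOVA. Power comes from the noncentral t with noncentrality 0.5 × √(n/2) / √variance.

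Two-arm path, 58 per arm with week-12 data:

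| ρ | Week-12 ANOVA | Change ANOVA | ANCOVA | Gain over week-12 | Gain over change |
|---|---|---|---|---|---|
| 0.3 | 76.1% | 61.7% | 79.9% | 3.8 | 18.2 |
| 0.5 | 76.1% | 76.1% | 86.9% | 10.8 | 10.8 |
| 0.7 | 76.1% | 93.1% | 96.2% | 20.1 | 3.1 |
| 0.8 | 76.1% | 98.8% | 99.4% | 23.3 | 0.6 |

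On the three-arm path, with 46 per arm, week-12 ANOVA has 66.0% power and ANCOVA has 70.1, 78.2, 91.3 and 97.7% at the same four correlations.

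In sample-size terms, week-12 ANOVA needs 1/(1 − ρ²) times the ANCOVA sample: 1.10, 1.33, 1.96 and 2.78 times. Change ANOVA needs 2/(1 + ρ) times: 1.54, 1.33, 1.18 and 1.11 times.

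**Step 3. Scale.** This used 20,000 simulated lognormal trials per setting, with 58 per arm and a shift of 0.5 SD on the log scale.

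| Log-SD | Raw scale | Log scale | Difference |
|---|---|---|---|
| 0.25 | 75.0% | 76.3% | 1.3 |
| 0.5 | 70.8% | 76.0% | 5.2 |
| 0.8 | 64.2% | 76.5% | 12.3 |
| 1.0 | 57.2% | 76.5% | 19.3 |
| 1.2 | 50.3% | 76.1% | 25.8 |

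Type I error on the raw scale stayed at or below about 5%, so the cost of skew here is power and not false positives.

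**Step 4. Incomplete records.** Assume equal correlation between visits, 15% lost before week 6 and 15% after. With ρ = 0.5, the variance of the week-12 contrast is 0.0258 for complete-case ANCOVA and 0.0253 for a model that keeps week-6-only participants. Across ρ = 0.3 to 0.8 the variance falls by about 1-4%, which is under 1 power point. A separate simulation of a GGT-like marker put the gain at 0-2 points. For measures taken only at baseline and week 12, a mixed model and complete-case ANCOVA have the same variance (0.0258 each at ρ = 0.5), so no precision is recovered.

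**The case against.** The best reply is that the plan is brief, not wrong. A reader might infer that it drops everyone with an incomplete record, analyses skewed levels untransformed, and so contradicts its own promise on missing data. The text supports none of this as fact. It says nothing on case deletion or scale, and the word ANOVA could cover a change score or a mixed-model analysis. The commitment in section 3.3.d and its sensitivity analyses are not confined to drinks per drinking day, so they can be read as filling the gap. Samples at exit also soften the loss. All of that stands, which is why the point is under-specification and tension. It does not remove the absence of a baseline covariate, and sensitivity analyses do not settle what the main analysis is.

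A second tempting inference is that much of the power is lost for every listed measure. For a GGT-like marker with an assumed log-SD of 0.9, correlation of 0.8, a true 25% fall and 71% versus 57% completion, simulated power is about 41% for ANOVA on raw change in completers and 77% for a baseline-adjusted log-scale repeated-measures model. Most of that gap is the log scale. At log-SD 0.5, with the same correlation, raw-change ANOVA and log ANCOVA in completers have about 96% and 99.8%; at 0.3 there is no difference. Nothing was simulated for cognition, and the documents give no SD for these markers.

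A third point also stands: ANCOVA for the two-visit measures omits people without a final value, just as ANOVA would. The gain there is baseline adjustment, not recovered participants.

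**Conclusion.** The point holds as a free improvement in method and specification. With 83 per arm, 70% completion and an effect of 0.5 SD, baseline adjustment takes power from 76% to 80-99% when compared with week-12 ANOVA, and gains under 1 to 18 points over change-score ANOVA, for assumed correlations of 0.3-0.8. The log scale may add about 1-26 points, depending on unknown skew. These two ranges come from separate calculations and should not be summed. Keeping week-6-only participants adds at most about 2 points; its main benefit is validity when dropout is missing at random.

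No stated power figure is wrong, and these are not primary endpoints. A reader might treat GGT and CDT as the only objective check on drinking, but AST and ALT are in the same laboratory group, and no passage makes any biomarker a condition for accepting the primary result.

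**What to change.** Replace the ANOVA sentence in section 3.3.c with three statements.

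1. **GGT, CDT, AST and ALT:** a likelihood-based repeated-measures model for the log level at weeks 6 and 12, with arm, week, arm-by-week, baseline log level, drinking stratum and site. Report the week-12 ratio of geometric means for each retained drug against placebo, with its 95% confidence interval.
2. **Cognition, neurosteroid and choline levels:** ANCOVA on the final value with the baseline value as covariate, on the log scale for skewed blood levels.
3. **Missing and off-schedule samples:** say how samples taken at early exit enter each model, and whether the sensitivity analyses in section 3.3.d apply to these measures.

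The cost is SAP wording, ideally fixed before any unblinded look. No new data or visits are needed. The one change for readers is that results on the log scale appear as ratios instead of unit differences.

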3.3. Approach

3.3.a. Preliminary Studies: The investigative team has extensive experience conducting clinical trials in this dual diagnosis population. Staff members at both sites have extensive experience conducting research in this population. Four studies directly pertinent to the current proposal are discussed below.

Pilot Study 1: A 12-week randomized, placebo-controlled, add-on, trial of citicoline

Methods: 44 outpatients with BPD and cocaine dependence were randomized to citicoline (2000 mg/day) or placebo.

Results: Those who took placebo had 6.41 times greater odds of testing positive for cocaine at exit than those who took citicoline. Days of cocaine use decreased with citicoline treatment, but increased with placebo (Cohen's d=0.6, medium effect size). The citicoline group had significantly (p = 0.006) better performance on the Rey Auditory Verbal Learning Test (RAVLT), an alternative word list (declarative memory). The Stroop Color test (executive functioning, attention, impulsivity) showed greater improvement with citicoline than placebo (2.8 ± 7.4 vs. -1.1 ± 4.6, p=0.04, Cohen's d=0.6). Study completion rates were over twice as high with citicoline as placebo. Side effects scale scores were significantly lower with citicoline than placebo (8.9 ± 1.5 vs. 9.8 ± 1.5, p<0.001).

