3.3.b.1. Details of Proposed Experiment: A 12-week, randomized, double-blind, parallel-group, placebocontrolled adaptive, DTL design clinical trial of citicoline and pregnenolone will be conducted in 199 outpatients with bipolar I or II disorder or schizoaffective disorder, bipolar type and current alcohol use disorder. Potential participants will be identified through physician referral, flyers, and brochures at clinics that treat the population needed for this study. In most cases the potential participant will call our clinic. At this time an appointment will be arranged, informed consent will be obtained, and assessment procedures, including a review of inclusion and exclusion criteria, will be performed.

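### Adverse events are compared as crude proportions with no allowance for time on study; if the largest pilot's retention recurs, citicoline's crude incidence would be inflated by about 7–11%

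*Combined protocol and SAP*

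**What the plan says.** Section 3.3.c (Statistical Methods) plans an adverse-event table at each stage, by seriousness, severity and possible relation to study drug. On the comparison between arms it says: "If appropriate, the incidence rate of adverse events will be compared by" Fisher's exact test. The general rule follows that "tests of hypotheses are 2-sided and the nominal level of significance will be 0.05". No person-time denominator and no time-to-event method is given for adverse events.

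Other parts of the plan bear on the point:

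- **Retention on citicoline.** Section 3.3.a, Pilot Study 1 (n=44): "Study completion rates were over twice as high with citicoline as placebo". Section 3.1.f reports a similar doubling in the methamphetamine trial (n=48) and lists better retention among the reasons for choosing the drug. Pilot Study 2 (n=130) gives 71% completion on citicoline and 57% on placebo, described as a non-significant difference.
- **Retention on pregnenolone.** Pilot Study 4 reports it as similar to placebo.
- **Expected completion here.** Section 3.3.d anticipates more than 70%.
- **Other tolerability analyses.** Section 3.3.c analyses side effects (exploratory aim 2) by a method similar to the primary GEE, and compares weeks in the study by Cox regression. Table 2 schedules the SAFTEE at the second baseline visit and every week to week 12.
- **Use at the interim.** Section 3.3.c (Sample size re-estimation) adds to the continuation rules: "This assumes that the DSMB assessment determines that the selected treatment(s) has an adequate safety and tolerability profile to continue the trial".

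**The concern.** The plan calls the quantity a rate, but Fisher's test takes only the number of participants with and without an event. A participant who stays 12 weeks has more chances to report an event than one who leaves at week 3, and the test treats them alike. If one arm is retained better, its crude incidence rises relative to the other even when the weekly risk is the same. An arm that people leave early is flattered.

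The sponsor treats retention as something citicoline may improve, and plans a Cox model to look at it, but the adverse-event comparison proceeds as if retention were equal. At stake is a foreseeable tilt, against citicoline, in a table produced at the end of each stage. The DSMB judges safety and tolerability at the interim. Pilot Study 1 reported lower side-effect scores on citicoline; a crude comparison of incidence would tend to hide part of any such advantage.

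**Working it through.** The plan states no figure for the adverse-event comparison, so there is none to reproduce. The pilot's description can be checked: with the post-baseline denominators (60 and 61), 71% and 57% are about 43/60 and 35/61, and Fisher's test gives p = 0.13, which agrees with non-significant.

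**Inputs.** Follow-up is 12 weeks (section 3.3.b.1). Completion S is 0.71 on citicoline and 0.57 on placebo (Pilot Study 2). There are 33 per arm at Stage 1; a retained arm would have 33 + 50 = 83 after Stage 2. Two inputs are assumed: a constant dropout hazard k, and the same constant weekly event hazard h in both arms.

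**Exposure.** k = −ln(S)/12 and mean weeks on study = (1 − S)/k.

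- Citicoline: k = 0.0285; 0.29/0.0285 = 10.2 weeks.
- Placebo: k = 0.0468; 0.43/0.0468 = 9.2 weeks.
- Ratio 1.107.

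**Crude incidence.** p = h/(h + k) × [1 − exp(−12(h + k))].

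| Weekly hazard h | Risk over a full 12 weeks | Citicoline | Placebo | Crude ratio |
|---|---|---|---|---|
| 0.02 | 21% | 18.2% | 16.5% | 1.102 |
| 0.05 | 45% | 38.9% | 35.5% | 1.095 |
| 0.10 | 70% | 61.2% | 56.4% | 1.084 |

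Across full-course risks from 10% to 90% the ratio runs from 1.105 to 1.067; for very rare events it approaches the exposure ratio, 1.107. Hence about 7–11%. The true rate ratio is 1.00 throughout. First events divided by time at risk recover it: at h = 0.05, mean time to first event or exit is [1 − exp(−12(h + k))]/(h + k) = 7.77 weeks on citicoline and 7.10 on placebo, and 0.389/7.77 = 0.355/7.10 = 0.05.

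**Sensitivity to timing.**

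- Events confined to the first three weeks: replace 12 by 3 in the exponent. At a 25% three-week risk (h = 0.0959) the figures are 24.0% v 23.4%, ratio 1.026. For three-week risks of 5% to 50% the ratio is 1.02–1.03.
- Uniform dropout: exposure ratio (1 + 0.71)/(1 + 0.57) = 1.089.
- All dropout at week 3: (0.71×12 + 0.29×3)/(0.57×12 + 0.43×3) = 9.39/8.13 = 1.155. All at week 9: 11.13/10.71 = 1.039.

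**Effect on the test.** With equal hazards, 71/57 completion and h from 0.02 to 0.10, exact enumeration gives a chance of two-sided Fisher p < 0.05 against citicoline of about 2–4% at 33 per arm and 3–7% at 83 per arm. The nominal figure is 2.5% per side.

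**Doubled completion.** The documents give no absolute rates, so 70% v 35% is an assumption. It gives 10.1 v 7.4 weeks and, at h = 0.05, 38.6% v 29.4%, ratio 1.31 (1.27–1.34 over the same hazards). Confined to the first three weeks it is about 1.08–1.09. With pregnenolone equal to placebo, overall Stage 1 completion would be (70 + 35 + 35)/3 = 47%. More generally, citicoline completion c with c/2 in the other two arms averages 2c/3; for that to exceed 0.70, c would have to exceed 1.05, which is impossible.

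**The case against.** The strongest reply is that the supported effect is small and the plan does not lean on this test. The only completion rates given are 71% and 57%, their difference was not significant, and at h = 0.05 they imply 3.4 percentage points. Constant hazard is an assumption that matters: doses rise through week 3, and if events cluster there the inflation is about 3%. All of this stands.

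Tolerability is also examined in other ways. The GEE-type analysis compares side-effect burden at attended visits, so a longer stay does not by itself accumulate events; the Cox model shows differential retention; and events leading to discontinuation, and serious events, receive separate attention. This stands in part. Those analyses do not adjust the adverse-event table, and the Cox result is not carried into it. The missing-data sensitivity analyses in section 3.3.d concern repeated measurements, not adverse events.

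Crude incidence over a fixed 12-week course is a legitimate description, and a person-time rate has its own assumption of constant risk. That is a reason to show both, not to omit one.

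Three stronger readings are not supported:

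- A reader might take 30% inflation as the prediction. It rests on assumed completion rates that cannot meet the plan's overall expectation in three-arm Stage 1 if pregnenolone is retained like placebo.
- A reader might take Fisher's test as the trial's decisive safety comparison, able to drop an arm. It is conditional, it sits beside other analyses, and safety at the interim is left to DSMB judgement with no adverse-event threshold or p-value.
- A reader might extend the bias to both drugs. Pilot Study 4 gives no reason to expect it for pregnenolone.

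**Conclusion.** The concern holds in a limited form. The named comparison ignores time on study, and the sponsor's own data make the direction of the resulting bias foreseeable for citicoline. If Pilot Study 2's completion recurs, with constant dropout and equal constant weekly hazards, crude incidence on citicoline is inflated by about 7–11%; early clustering of events cuts this to about 3%, and other dropout shapes move the exposure ratio between about 1.04 and 1.15. False significance against citicoline would be uncommon. The harm is mainly a tilted estimate in a table available at the interim and at the end, not a likely wrong decision. It merits correction because the correction is cheap and needs no new data.

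**What to change.** In section 3.3.c, keep the counts by arm and keep Fisher's test as a descriptive supplement. Add, for each event type and arm, the number of first events per person-week on study drug, counting time to the first event or the end of study drug, with the rate ratio and exact (Poisson) 95% CI against placebo. A time-to-first-event analysis would serve equally. Show weeks 0–3 and weeks 4–12 separately, so that events concentrated during titration are not averaged away. Use the same table at the interim DSMB review and at the end of the trial, and replace the phrase that makes the comparison conditional with a stated criterion.

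The cost is SAP wording and one extra column per table. Time in study is already needed for the planned Cox regression. The downside is an assumption of constant rate within each of the two periods, and wide intervals at 33 per arm for uncommon events.
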